4089459	AV nodal re-entry tachycardia
4228836	AV node arrhythmia
4088983	AV-junctional (nodal) bradycardia
4091901	Aberrant premature complexes
4092011	Aberrantly conducted complex
4057008	Accelerated atrioventricular conduction
4247537	Accelerated idioventricular rhythm
37312140	Acquired Brugada syndrome
37116420	Acquired complete atrioventricular block
40479264	Acquired long QT syndrome
4224848	Andersen Tawil syndrome
35608001	Ankyrin-B syndrome
313224	Anomalous atrioventricular excitation
4296729	Anterior fascicular block, posterior fascicular block AND incomplete right bundle branch block
4121481	Antidromic atrioventricular re-entrant tachycardia
37109912	Arrhythmia due to and following acute myocardial infarction
43020930	Arrhythmia due to vegetation of infective endocarditis
37108582	Arrhythmia during surgery
4101624	Arrhythmogenic right ventricular dysplasia

	Phase II C3-002 – Study Protocol	
	Author(s): [name], [name], [name]	Version: v2.1
		Dissemination level: Public

4102252	Asymptomatic sinoatrial node dysfunction
4068155	Atrial arrhythmia
4088504	Atrial bigeminy
4088986	Atrial escape complex
313217	Atrial fibrillation
4108832	Atrial fibrillation and flutter
44782442	Atrial fibrillation with rapid ventricular response
314665	Atrial flutter
4088987	Atrial parasystole
4108830	Atrial paroxysmal tachycardia
4115173	Atrial premature complex
37110775	Atrial septal defect, atrioventricular conduction defect syndrome
42872924	Atrial standstill
4171269	Atrial tachycardia
4091903	Atrial trigeminy
316135	Atrioventricular block
43020929	Atrioventricular block due to endocarditis
4305210	Atrioventricular conduction disorder
4175473	Atrioventricular dissociation
42536726	Atrioventricular reciprocating tachycardia
4081675	Atrioventricular tachycardia
36712986	Atypical atrial flutter
4250169	Bifascicular block
321587	Bilateral bundle branch block
4088984	Blocked premature atrial contraction
4228448	Bradycardia
4169095	Bradycardia
45766074	Bradycardic cardiac arrest
4303408	Brugada syndrome
313791	Bundle branch block
40484036	Bundle branch reentrant ventricular tachycardia
44784217	Cardiac arrhythmia
38001137	Cardiac arrhythmia & conduction disorders w CC
38001138	Cardiac arrhythmia & conduction disorders w/o CC/MCC
44784234	Cardiac arrhythmia associated with genetic disorder
45757098	Cardiac arrhythmia in mother complicating childbirth
44784235	Cardiac channelopathy
4303238	Catecholaminergic polymorphic ventricular tachycardia
42536725	Cavotricuspid isthmus dependent macroreentry tachycardia
36715042	Chronic atrial and intestinal dysrhythmia
4141360	Chronic atrial fibrillation
4137382	Chronic atrial flutter
4098133	Chronic ectopic atrial tachycardia

	Phase II C3-002 – Study Protocol	
	Author(s): [name], [name], [name]	Version: v2.1
		Dissemination level: Public

320744	Complete atrioventricular block
46269694	Complete atrioventricular block as complication of atrioventricular nodal ablation
4267892	Complete left bundle branch block
4088337	Complete right bundle branch block
4121615	Concealed accessory pathway
316999	Conduction disorder of the heart
4117112	Controlled atrial fibrillation
4304839	Diffuse intraventricular block
4236004	Ectopic atrial beats
4121479	Ectopic atrial tachycardia
4121480	Ectopic atrioventricular node tachycardia
4143042	Ectopic beats
4164083	Ectopic rhythm
4122762	Electromechanical dissociation
4148028	Electromechanical dissociation with successful resuscitation
36675005	Extrasystoles, short stature, hyperpigmentation, microcephaly syndrome
37395821	Familial atrial fibrillation
35624231	Familial dilated cardiomyopathy with conduction defect due to LMNA mutation
37399476	Familial isolated arrhythmogenic right ventricular dysplasia
4121613	Familial isolated complete right bundle branch block
4119603	Familial sick sinus syndrome
4124703	Familial ventricular tachycardia
4305862	Fascicular ventricular tachycardia
4226399	Fibrillation
314379	First degree atrioventricular block
4029303	Fusion beats
46284985	HHS - holiday heart syndrome
320425	Heart block
40481891	Heart block due to drug
36715370	Heart-hand syndrome type 2
36717434	Heart-hand syndrome type 3
43020494	High degree second degree atrioventricular block
4120086	His bundle tachycardia
4078058	Holt-Oram syndrome
4320474	Idiojunctional tachycardia
37109917	Idiopathic ventricular fibrillation not Brugada type
4171193	Idioventricular rhythm
4137871	Inappropriate sinus tachycardia
4124697	Incessant atrial tachycardia
4119600	Incessant infant ventricular tachycardia
4304095	Incisional tachycardia
4298806	Incomplete atrioventricular block with atrioventricular response
4088336	Incomplete left bundle branch block

	Phase II C3-002 – Study Protocol	
	Author(s): [name], [name], [name]	Version: v2.1
		Dissemination level: Public

4088338	Incomplete right bundle branch block
4121482	Induced ventricular tachycardia
4088332	Intermittent second degree atrioventricular block
4243143	Interpolated PVCs
4166844	Intraventricular conduction defect
4221549	Irregular tachycardia
4161597	Jervell and Lange-Nielsen syndrome
4091899	Junctional ectopic tachycardia
4166380	Junctional escape beats
4218739	Junctional premature beats
4088351	Junctional premature complex
4295336	Left anterior fascicular block
4171887	Left atrial incisional tachycardia
316998	Left bundle branch block
313209	Left bundle branch hemiblock
4111543	Left main stem bundle branch block
4268046	Left posterior fascicular block
4153404	Lev's syndrome
4119601	Lone atrial fibrillation
314664	Long QT syndrome
37396235	Long QT syndrome caused by drug
37117768	Long thumb brachydactyly syndrome
45768480	Longstanding persistent atrial fibrillation
437892	Lown-Ganong-Levine syndrome
42536724	Macro re-entrant atrial tachycardia
46272503	Mahaim fiber tachycardia
4088347	Marked sinus arrhythmia
35608087	Microcephalus, cerebellar hypoplasia, cardiac conduction defect syndrome
4088496	Minor intraventricular conduction defect
4205137	Mobitz type I incomplete atrioventricular block
313780	Mobitz type II atrioventricular block
4034164	Monofascicular block
4023336	Multifocal PVCs
4176112	Multifocal atrial tachycardia
4271464	Multifocal premature beats
4089460	Multiple atrial premature complexes
4088985	Multiple premature ventricular complexes
4089463	Multiple ventricular interpolated complexes
4088982	Narrow QRS ventricular tachycardia
37398927	Naxos disease
4217221	Nodal rhythm disorder
42539038	Non-cavotricuspid isthmus dependent atrial tachycardia
4119602	Non-rheumatic atrial fibrillation

	Phase II C3-002 – Study Protocol	
	Author(s): [name], [name], [name]	Version: v2.1
		Dissemination level: Public

44784220	Non-specific intraventricular conduction delay
4191222	Nonparoxysmal AV nodal tachycardia
44782789	Nonsustained paroxysmal supraventricular tachycardia
44782707	Nonsustained paroxysmal ventricular tachycardia
40480274	Nonsustained ventricular tachycardia
4124700	Orthodromic atrioventricular re-entrant tachycardia
4030583	Pacemaker twiddler's syndrome
4089464	Paired ventricular premature complexes
4006208	Parasystole
4154290	Paroxysmal atrial fibrillation
4146580	Paroxysmal atrial flutter
4190306	Paroxysmal atrial tachycardia with block
4108241	Paroxysmal atrioventricular tachycardia
4119604	Paroxysmal familial ventricular fibrillation
4111546	Paroxysmal junctional tachycardia
4111698	Paroxysmal nodal tachycardia
317893	Paroxysmal supraventricular tachycardia
313792	Paroxysmal tachycardia
437579	Paroxysmal ventricular tachycardia
4111570	Partial atrioventricular block
4232691	Permanent atrial fibrillation
4124702	Permanent junctional reciprocating tachycardia
4232697	Persistent atrial fibrillation
4258998	Persistent sinus bradycardia
4124701	Postoperative His bundle tachycardia
43020495	Postoperative atrioventricular block
4119605	Postoperative complete heart block
4124704	Postoperative sinus node dysfunction
42539346	Preexcited atrial fibrillation
4109365	Premature atrial contraction
316429	Premature beats
44784218	Progressive familial heart block
44784219	Progressive familial heart block, type IB
44782643	Progressive familial heart block, type II
4233619	Pulseless ventricular tachycardia
4199501	Rapid atrial fibrillation
4124696	Re-entrant atrial tachycardia
4124698	Re-entrant atrioventricular node tachycardia
4124699	Re-entrant atrioventricular tachycardia
4111552	Re-entry ventricular arrhythmia
45771051	Recurrent ventricular tachycardia
4302802	Right atrial incisional tachycardia
4249027	Right branch block, incomplete anterior fascicular block AND incomplete posterior fascicular block

	Phase II C3-002 – Study Protocol	
	Author(s): [name], [name], [name]	Version: v2.1
		Dissemination level: Public

314059	Right bundle branch block
4184950	Right bundle branch block AND incomplete left bundle branch block
316432	Right bundle branch block AND left anterior fascicular block
321590	Right bundle branch block AND left posterior fascicular block
4138973	Right bundle branch block with left bundle branch block
4244693	Right bundle branch block, anterior fascicular block AND incomplete left bundle branch block
4217860	Right bundle branch block, anterior fascicular block AND incomplete posterior fascicular block
4138545	Right bundle branch block, anterior fascicular block AND posterior fascicular block
4280348	Right bundle branch block, posterior fascicular block AND incomplete anterior fascicular block
4032785	Right bundle branch block, posterior fascicular block AND incomplete left bundle branch block
4121483	Right ventricular outflow tract ventricular tachycardia
4049219	Romano-Ward syndrome
4089461	Run of atrial premature complexes
4091904	Run of ventricular premature complexes
37312595	Scar mediated macro re-entrant atrial tachycardia
318448	Second degree atrioventricular block
4169261	Severe sinus bradycardia
44784236	Short QT syndrome
4261842	Sick sinus syndrome
4028322	Sinoatrial arrest with nodal/ventricular escape
4277903	Sinoatrial block
4303256	Sinoatrial nodal reentrant tachycardia
36674897	Sinoatrial node dysfunction and deafness
4120084	Sinoatrial node tachycardia
4210313	Sinus arrest
4088352	Sinus arrest with atrial escape
4088210	Sinus arrest with junctional escape
4091446	Sinus arrest with ventricular escape
4171683	Sinus bradycardia
317302	Sinus node dysfunction
4088350	Slow ventricular response
4188347	Stokes-Adams syndrome
4248028	Supraventricular arrhythmia
4091902	Supraventricular bigeminy
42538755	Supraventricular bradyarrhythmia
441872	Supraventricular premature beats
4275423	Supraventricular tachycardia
4120085	Supraventricular tachycardia with functional bundle branch block
4325850	Sustained ventricular fibrillation
4139206	Sustained ventricular tachycardia
40480216	Symptomatic sinus bradycardia
315643	Tachyarrhythmia
4254116	Tachycardia-bradycardia

	Phase II C3-002 – Study Protocol	
	Author(s): [name], [name], [name]	Version: v2.1
		Dissemination level: Public

4262389	Tic-tac rhythm
44783199	Timothy syndrome type 1
36714606	Timothy syndrome type 2
37397458	Torsade de pointes with short coupling interval syndrome
37110729	Torsades de pointe caused by drug
4135823	Torsades de pointes
321315	Trifascicular block
36714994	Typical atrial flutter
4120087	Unidirectional retrograde accessory pathway
4099778	Unifocal PVCs
4106715	Vagal autonomic bradycardia
43021222	Vagal autonomic bradycardia of prematurity
4185572	Ventricular arrhythmia
4008580	Ventricular bigeminy
4327066	Ventricular escape beat
4088507	Ventricular escape complex
4218242	Ventricular escape rhythm
36714539	Ventricular extrasystoles with syncope, perodactyly and Robin sequence syndrome
437894	Ventricular fibrillation
4111700	Ventricular fibrillation and flutter
433225	Ventricular flutter
4092010	Ventricular interpolated complexes
4244893	Ventricular parasystole
4108828	Ventricular pre-excitation
4066289	Ventricular premature beats
4089462	Ventricular premature complex
4088506	Ventricular quadrigeminy
40622721	Ventricular tachyarrhythmia
4103295	Ventricular tachycardia
4119599	Ventricular tachycardia with normal heart
4091900	Ventricular tachycardia, monomorphic
4088349	Ventricular tachycardia, polymorphic
4088501	Ventricular tachycardia, polymorphic without Q-T prolongation
4088505	Ventricular trigeminy
4088348	Wide QRS ventricular tachycardia
4086313	Withdrawal arrhythmia
40483798	Bifascicular block on electrocardiogram
4064452	ECG: atrial fibrillation
4065290	ECG: partial atrioventricular block - 2:1
4064458	ECG: partial atrioventricular block - 3:1
4064873	ECG: partial atrioventricular block - long PR
4065289	ECG: partial sinoatrial block
4138456	ECG: sinus bradycardia

	Phase II C3-002 – Study Protocol	
	Author(s): [name], [name], [name]	Version: v2.1
		Dissemination level: Public

4138921	EKG: Mobitz type II atrioventricular block
4065285	EKG: atrial ectopics
4065288	EKG: atrial flutter
4064874	EKG: complete atrioventricular block
4064872	EKG: complete sinoatrial block
4064457	EKG: heart block
4064453	EKG: ventricular arrhythmia
4064455	EKG: ventricular fibrillation
4064869	Electrocardiogram: paroxysmal atrial tachycardia
40482086	Left anterior fascicular block on electrocardiogram
40482505	Left posterior fascicular block on electrocardiogram
4064459	Mobitz type I second degree atrioventricular block on electrocardiogram
4061093	O/E - pulse rate - bradycardia
40482887	Right bundle branch block and left anterior fascicular block on electrocardiogram
40483359	Right bundle branch block and left posterior fascicular block on electrocardiogram
40482938	Trifascicular block on electrocardiogram

	Phase II C3-002 – Study Protocol	
	Author(s): [name], [name], [name]	Version: v2.1
	Dissemination level: Public	

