8.6.2. Outcomes

Primary outcomes of interest:

1. COVID-19 related hospitalisation
2. COVID-19 related death
3. All-cause mortality in the 3 months after discharge from a COVID-19 hospitalisation
4. All-cause mortality in the 6 months after discharge from a COVID-19 hospitalisation
5. Incidence of new-onset type 1 Diabetes Mellitus beyond the first 30d after SARS-CoV-2 infection
6. Incidence of new-onset type 2 Diabetes Mellitus beyond the first 30d after SARS-CoV-2 infection
7. Incidence of cardiovascular events (cerebrovascular disorders, dysrhythmias, ischemic and non-ischemic heart disease, pericarditis, myocarditis, heart failure and thromboembolic disease) in the 12 months after a SARS-CoV-2 infection.

Preliminary code lists are available in the appendix of this protocol for all outcomes.

SARS-CoV-2 infection and COVID-19

Positive test result for SARS-CoV-2

RT-PCR tests have high sensitivity and specificity for SARS-CoV-2. However, as a result of changes in the availability of population wide RT-PCR and home self-reported lateral flow tests during the Omicron period, it may not be possible to exclusively use RT-PCR tests when identifying positive test results in all datasets. All positive test results for SARS-CoV-2 observable in the database will therefore be included for the primary analysis, with documentation of what type of test it was to allow sensitivity analysis restricted to RT-PCR diagnosed patients as needed.

Clinical diagnosis of COVID-19

Whilst testing for SARS-CoV-2 was commonly performed in some of the countries that will be represented in this study, clinical diagnoses of COVID-19 were also made for many individuals. Diagnostic codes compatible with COVID-19 will therefore also be identified, with the recorded date being used in the analyses.

Hospitalization with COVID-19

Patients hospitalized with COVID-19 will be identified based on having a hospitalization along with a confirmatory diagnosis or test result of COVID-19 (both as defined above) within a time window from 21 days prior to admission up to three days following their admission. This time window has been chosen in accordance with previous studies commissioned by the EMA, and aimed to include those who had the diagnosis made prior to their hospitalization and to allow for a delay in test results or diagnoses to be made or recorded, while excluding individuals with hospital-acquired COVID-19.

COVID-19 related death

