8.8.6 Stratified analyses, subgroup analyses and sensitivity analyses

All analyses will be stratified separately by vaccine brand (Comirnaty and Spikevax), and age at index date (i.e. age <65 years, ≥65 years).

Subgroup analyses will be conducted among people with immunocompromised status, recorded within 365 days prior to index date.

No sensitivity analyses are planned (Table 8.8.6.1).

Table 8.8.6.1 Sensitivity analyses – rationale, strengths and limitations

	What is being varied? How?	Why? (What do you expect to learn?)	Strengths of the sensitivity analysis compared to the primary	Limitations of the sensitivity analysis compared to the primary

	Phase II C3-002 – Study Protocol	
	Author(s): [name], [name], [name]	Version: v2.1
		Dissemination level: Public

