APPENDIX I – PRELIMINARY CONCEPTS FOR STUDY VARIABLES

Table 1: Preliminary concepts for COVID-19 Diagnosis and SARS-CoV-2 infection

Concept Id	Concept name	domain
3661405	Acute bronchitis caused by SARS-CoV-2	Condition
3655976	Acute hypoxemic respiratory failure due to disease caused by Severe acute respiratory syndrome coronavirus 2	Condition
3661748	Acute kidney injury due to disease caused by Severe acute respiratory syndrome coronavirus 2	Condition
3661406	Acute respiratory distress syndrome due to disease caused by Severe acute respiratory syndrome coronavirus 2	Condition
3662381	Asymptomatic SARS-CoV-2	Condition
756031	Bronchitis caused by COVID-19	Condition
3656667	Cardiomyopathy due to disease caused by Severe acute respiratory syndrome coronavirus 2	Condition
3656668	Conjunctivitis due to disease caused by Severe acute respiratory syndrome coronavirus 2	Condition
439676	Coronavirus infection	Condition
37311061	COVID-19	Condition
4100065	Disease due to Coronaviridae	Condition
3656669	Dyspnea caused by Severe acute respiratory syndrome coronavirus 2	Condition
37310284	Encephalopathy due to disease caused by Severe acute respiratory syndrome coronavirus 2	Condition
3661885	Fever caused by Severe acute respiratory syndrome coronavirus 2	Condition
37310283	Gastroenteritis caused by SARS-CoV-2 (severe acute respiratory syndrome coronavirus 2)	Condition
37310286	Infection of upper respiratory tract caused by Severe acute respiratory syndrome coronavirus 2	Condition
3663281	Lower respiratory infection caused by SARS-CoV-2	Condition
3661631	Lymphocytopenia due to Severe acute respiratory syndrome coronavirus 2	Condition
37310287	Myocarditis due to disease caused by Severe acute respiratory syndrome coronavirus 2	Condition
37310254	Otitis media due to disease caused by Severe acute respiratory syndrome coronavirus 2	Condition
704995	Patient meets COVID-19 clinical diagnostic criteria	Observation
700297	Patient meets COVID-19 laboratory confirmation criterion (detection of specific RNA in a clinical specimen using a molecular amplification detection test)	Observation
704996	Patient meets COVID-19 laboratory diagnostic criteria	Observation
700296	Patient meets COVID-19 presumptive laboratory evidence criteria (detection of specific antigen in a clinical specimen, OR detection of specific antibody in serum, plasma, or whole blood indicative of a new or recent infection)	Observation
37016927	Pneumonia caused by Human coronavirus	Condition

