3661408	Pneumonia caused by SARS-CoV-2	Condition
40479642	Pneumonia due to Severe acute respiratory syndrome coronavirus	Condition
756039	Respiratory infection caused by COVID-19	Condition

	Phase II C3-002 – Study Protocol	
	Author(s): [name], [name], [name]	Version: v2.1
	Dissemination level: Public	

3655977	Rhabdomyolysis due to disease caused by Severe acute respiratory syndrome coronavirus 2	Condition
3655975	Sepsis due to disease caused by Severe acute respiratory syndrome coronavirus 2	Condition
320651	Severe acute respiratory syndrome	Condition
37396171	Severe acute respiratory syndrome of upper respiratory tract	Condition
37311060	Suspected COVID-19	Observation
3661632	Thrombocytopenia due to Severe acute respiratory syndrome coronavirus 2	Condition
45763724	Suspected coronavirus infection	Observation
40218804	2019-ncov coronavirus, sars-cov-2/2019-ncov (covid-19), any technique, multiple types or subtypes (includes all targets), non-cdc	Measurement
40218805	Cdc 2019 novel coronavirus (2019-ncov) real-time rt-pcr diagnostic panel	Measurement
44789510	Coronavirus nucleic acid detection	Measurement
44811805	Coronavirus nucleic acid detection assay	Measurement
45770687	Coronavirus RNA (ribonucleic acid) detection assay	Measurement
44807536	Coronavirus RNA (ribonucleic acid) measurement by NAAT (nucleic acid amplification test)	Measurement
3667069	Detection of ribonucleic acid of Severe acute respiratory syndrome coronavirus 2 using polymerase chain reaction	Observation
36660491	Human coronavirus 229E RNA [Presence] in Lower respiratory specimen by NAA with non-probe detection	Measurement
36659667	Human coronavirus HKU1 RNA [Presence] in Lower respiratory specimen by NAA with non-probe detection	Measurement
36660329	Human coronavirus NL63 RNA [Presence] in Lower respiratory specimen by NAA with non-probe detection	Measurement
36660364	Human coronavirus OC43 RNA [Presence] in Lower respiratory specimen by NAA with non-probe detection	Measurement
742224	Infectious agent antigen detection by immunoassay technique, qualitative or semiquantitative, multiple-step method; severe acute respiratory syndrome coronavirus (eg, SARS-CoV, SARS-CoV-2 [COVID-19]) (Coronavirus disease [COVID-19])	Measurement
700360	Infectious agent detection by nucleic acid (DNA or RNA); severe acute respiratory syndrome coronavirus 2 (SARS-CoV-2) (Coronavirus disease [COVID-19]), amplified probe technique	Measurement

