702834	Measurement of Severe acute respiratory syndrome coronavirus 2 (SARS-CoV-2) specific cell-mediated immune response in Blood	Measurement
704992	Measurement of Severe acute respiratory syndrome coronavirus 2 (SARS-CoV-2) using Culture method	Measurement
705001	Measurement of Severe acute respiratory syndrome coronavirus 2 (SARS-CoV-2) using Nucleic acid amplification technique	Measurement
705000	Measurement of Severe acute respiratory syndrome coronavirus 2 (SARS-CoV-2) using Nucleic acid amplification technique in Blood	Measurement
756085	Measurement of Severe acute respiratory syndrome coronavirus 2 (SARS-CoV-2) using Nucleic acid amplification technique in Respiratory specimen	Measurement
586308	Measurement of Severe acute respiratory syndrome coronavirus 2 (SARS-CoV-2) using Nucleic acid amplification technique in Saliva	Measurement
705106	Measurement of Severe acute respiratory syndrome coronavirus 2 (SARS-CoV-2) using Nucleic acid amplification technique in Sample from nose	Measurement
704975	Measurement of Severe acute respiratory syndrome coronavirus 2 (SARS-CoV-2) using Nucleic acid amplification technique in Sample from oropharynx	Measurement
756084	Measurement of Severe acute respiratory syndrome coronavirus 2 (SARS-CoV-2) using Nucleic acid amplification technique in Unspecified specimen	Measurement
704993	Measurement of Severe acute respiratory syndrome coronavirus 2 (SARS-CoV-2) using Sequencing	Measurement
723477	SARS-CoV-2 (COVID-19) Ag [Presence] in Respiratory specimen by Rapid immunoassay	Measurement
706167	SARS-CoV-2 (COVID-19) N gene [Cycle Threshold #] in Unspecified specimen by NAA with probe detection	Measurement
706157	SARS-CoV-2 (COVID-19) N gene [Cycle Threshold #] in Unspecified specimen by Nucleic acid amplification using CDC primer-probe set N1	Measurement
706155	SARS-CoV-2 (COVID-19) N gene [Cycle Threshold #] in Unspecified specimen by Nucleic acid amplification using CDC primer-probe set N2	Measurement
715272	SARS-CoV-2 (COVID-19) N gene [Presence] in Nasopharynx by NAA with probe detection	Measurement
757678	SARS-CoV-2 (COVID-19) N gene [Presence] in Nose by NAA with probe detection	Measurement
706161	SARS-CoV-2 (COVID-19) N gene [Presence] in Respiratory specimen by NAA with probe detection	Measurement

	Phase II C3-002 – Study Protocol	
	Author(s): [name], [name], [name]	Version: v2.1
	Dissemination level: Public	

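### The preliminary COVID-19 concept list contains entries that do not show SARS-CoV-2 infection and do not match the case definitions in section 8.6.2; list and text should be reconciled and a confirmed-case analysis pre-specified

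*Protocol*

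**What the plan says.** **Case definitions (section 8.6.2).** A test counts if it is positive for SARS-CoV-2. A clinical diagnosis counts if its code is compatible with COVID-19. Hospitalisation requires "having a hospitalization along with a confirmatory diagnosis or test result of COVID-19", and the text refers back to those two definitions. COVID-19 related death, diabetes and cardiovascular events each need a clinical diagnosis or a positive test within a stated window.

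**The list (Appendix I).** It is headed "Table 1: Preliminary concepts for COVID-19 Diagnosis and SARS-CoV-2 infection". Among many specific SARS-CoV-2 concepts it contains:

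- RNA tests for four seasonal coronaviruses: "Human coronavirus 229E RNA [Presence] in Lower respiratory specimen by NAA with non-probe detection" and the matching entries for HKU1, NL63 and OC43;
- SARS-1 conditions (320651, 37396171, 40479642) and generic coronavirus conditions (439676, 4100065, 37016927);
- a measurement of "specific cell-mediated immune response in Blood" (702834);
- "Suspected COVID-19" (37311060) and a suspected-coronavirus code (45763724);
- a presumptive-evidence concept (700296) met by antigen or by "detection of specific antibody in serum, plasma, or whole blood indicative of a new or recent infection".

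**Code review (section 10).** COVID-19 codes come from lists used in earlier studies, updated to add newer codes. Clinician exclusion of irrelevant codes is described for outcome conditions, with diabetes as the example.

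**Sensitivity analyses.** Section 8.6.2 has test type documented "to allow sensitivity analysis restricted to RT-PCR diagnosed patients as needed". Section 8.8.6 says "No sensitivity analyses are planned". The ENCePP checklist marks outcome validity (6.3), control of outcome misclassification (10.6) and sensitivity analyses (10.8) as not applicable.

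**The concern.** A programmer who followed the table as printed could count as COVID-19 an infection with another coronavirus, an immune response, or a suspicion that was never confirmed.

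The reach is wide. All seven outcomes need a COVID-19 or SARS-CoV-2 record. One such record in the 21 days before to 3 days after admission turns any admission into a COVID-19 hospitalisation, and one within 28 days before death turns a death into a COVID-19 death. The same record drives the 90-day eligibility exclusion and the matching variable for previous COVID-19.

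A vaccine effect on SARS-CoV-2 cannot be expected to show in events that are not SARS-CoV-2. With no sensitivity analysis planned, the report would give no indication of how much the estimates depend on these codes.

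**Working it through.** The protocol states no misclassification rate, event count or power, so there is no planned figure to reproduce. The main check is textual; the arithmetic only illustrates size.

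**Step 1. Each group of entries against section 8.6.2**

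| Entry | Applicable rule | Fits? |
|---|---|---|
| 229E, HKU1, NL63, OC43 RNA | positive test, for SARS-CoV-2 | No. A positive result shows a different virus. |
| SARS-1 conditions | code compatible with COVID-19 | No. A different disease. |
| Generic coronavirus conditions | code compatible with COVID-19 | Not specific. Defensible only where a database records COVID-19 under them. |
| Cell-mediated immune response | positive test, for SARS-CoV-2 | No. It measures response, not current infection. |
| Two suspected codes | compatible (diagnosis); confirmatory (hospitalisation) | Arguable for the first, in conflict with the second. |
| Combined antigen-or-antibody concept | positive test or compatible diagnosis | Arguable. It is worded as new or recent infection. |

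**Step 2. Does the positive-result rule remove the problem?** Only in part. It can act on Measurement entries that carry a result, although a positive 229E or T-cell result still does not show SARS-CoV-2 infection. The suspected and generic codes are listed as Observations or Conditions. There the record itself makes the case, and no result filter applies.

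**Step 3. Size.** Let f be the share of comparator-arm events that are false positives, and R the rate ratio (extra dose versus comparator) for those false events. Then

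HR observed = (1 − f) × HR true + f × R, and VE = 1 − HR (Table 7.1).

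With R = 1 this reduces to VE observed = (1 − f) × VE true. Taking the 67.8% cited in section 6 as the true value:

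- f = 5%: 0.95 × 67.8 = 64.4%
- f = 10%: 0.90 × 67.8 = 61.0%
- f = 20%: 0.80 × 67.8 = 54.2%

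The values of f are assumed.

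**Step 4. If the false events differ by arm.** At f = 20% and true VE 67.8% (HR 0.322), the first term is 0.8 × 0.322 = 0.2576.

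- R = 1.5: 0.2576 + 0.30 = 0.5576, VE 44.2%
- R = 0.5: 0.2576 + 0.10 = 0.3576, VE 64.2%
- R = 0.3: 0.2576 + 0.06 = 0.3176, VE 68.2%

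At a waned true VE of 20% with f = 20% and R = 0.5, the HR is 0.8 × 0.8 + 0.10 = 0.74, so VE is 26.0%: inflated, not diluted. At a true VE of zero with the same f and R, the HR is 0.8 + 0.10 = 0.90 and VE appears as 10.0%. The direction is therefore not fixed.

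**The case against.** The strongest reply is that the table is a preliminary search list, not a case definition. It gives concept names without result values and even includes mixed influenza and SARS-CoV-2 panels, so a filter on positive SARS-CoV-2 results is plainly intended. Final lists may sit in documents not shown. Nothing shows how often the doubtful codes occur in the three databases, and section 11 already discusses outcome misclassification, mainly through under-recording.

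Much of this stands for result-bearing tests. It does not cover the Condition and Observation codes, and section 10 describes no pruning of COVID-19 codes.

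Four stronger readings are tempting, and the protocol does not support them:

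- **That the whole study promises confirmed cases.** The word confirmatory governs hospitalisation alone. Death, diabetes and cardiovascular events rest on a clinical diagnosis or positive test, and a diagnosis code need only be compatible with COVID-19. For suspected codes, the tension lies as much within section 8.6.2 as between it and the appendix.
- **That every effectiveness estimate is diluted.** This needs false events unrelated to dose and a true effect above zero. Step 4 shows that otherwise the bias can go either way.
- **That the antibody entry captures vaccine response.** It is one combined concept, worded as new or recent infection. Deleting it outright could also lose antigen-positive cases.
- **That an RT-PCR-only analysis would settle the matter, or that sections 8.6.2 and 8.8.6 flatly contradict each other.** The seasonal-coronavirus entries are themselves nucleic-acid tests, so a restriction by test type alone does not remove them. The RT-PCR restriction is foreseen only if needed.

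**Conclusion.** The point holds as a mismatch between the list and the text. The seasonal-coronavirus, SARS-1 and cell-mediated-immunity entries do not belong in a definition of SARS-CoV-2 infection. Generic coronavirus codes need a database-specific reason to stay. Suspected codes conflict with the hospitalisation wording and need an explicit decision.

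The effect on results cannot be sized from the protocol. If the false events are unrelated to dose and the true effect is above zero, the loss is proportional to f: 3.4, 6.8 and 13.6 percentage points from 67.8% at assumed shares of 5%, 10% and 20%. That benchmark concerns hospitalisation after a bivalent BA4/5 fourth dose, so it illustrates scale only and is no guide for death, diabetes or the comparison of one with two doses. If recording differs by arm, neither size nor direction is known, which is itself a reason for a confirmed-case check. The change is worth making before the code lists are finalised.

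**What to change.** 1. In Appendix I Table 1, remove the four seasonal-coronavirus tests, the SARS-1 conditions and the cell-mediated immune-response test from the outcome definition.
2. Remove the generic coronavirus concepts unless a named database maps COVID-19 to them; if so, record that.
3. In section 8.6.2, reconcile the confirmatory wording for hospitalisation with the compatible wording for diagnoses, and state for each outcome whether suspected codes count.
4. Repeat beside the table that Measurement concepts count only with a positive SARS-CoV-2 result.
5. In section 8.8.6, replace the statement that none is planned with a confirmed-case sensitivity analysis: a positive SARS-CoV-2 RT-PCR or antigen result, or a specific COVID-19 diagnosis. Exclude suspected codes, and exclude the combined antigen-or-antibody concept where antigen cannot be separated.

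The cost is an edited code list, one re-run per outcome and somewhat fewer events. Suspected codes and the combined concept need not be deleted from the primary definition; their influence can be shown in the sensitivity analysis.
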